## **5.7 Agent Administration**

Treatment will be administered on an outpatient basis. Reported adverse events and potential risks from the agents used in this protocol are described in Section [7](#). Appropriate dose modifications for these agents are described in Section [6](#). No investigational or commercial agents or therapies other than those described below may be administered with the intent to treat the patient's malignancy.

Patients in all treatment arms (Erlotinib, AZD6244, [MK2206](#), Lapatinib and Sunitinib) will be provided with a Medication Diary ([Appendix B](#)). They will be instructed in its use and asked to bring the diary with them to each appointment. A new copy of the Medication Diary will be given to patients whose dose is reduced due to adverse events. Patients should log in their daily dose onto the diary, including missed, skipped, or vomited doses. If the patient vomits after taking the tablets, the dose is replaced only if the tablets can actually be seen and counted. If a patient misses a dose, he or she should be instructed to resume dosing with the next scheduled dose.

### **5.7.1 CTEP agents**

#### **5.7.1.1 Erlotinib**

- 1) Erlotinib will be administered at a dose of 150 mg once daily every three weeks.

- 2) Tablets should be taken once daily preferably in the morning with up to 200 mL of water 1 hour before or 2 hours after food.
- 3) Patients should wear sunscreen protection, hat, and long sleeves to avoid sun as it can exacerbate skin rash.
- 4) Patients should be instructed to store Erlotinib at room temperature.
- 5) Patients should be advised to drink plenty of water or take rehydration fluids to avoid dehydration if diarrhea occurs.

#### **5.7.1.2 AZD6244 Hydrogen Sulfate**

- 1) AZD6244 hydrogen sulfate will be administered at a dose of 75 mg twice daily (BID), approximately 12 hours apart, every three weeks.
- 2) Advise the patient to take AZD6244 doses on an empty stomach (no food or drink other than water for 1 hour before or 2 hours after dosing).
- 3) Patients should be instructed to store AZD6244 at room temperature.
- 4) Patients should be advised to drink plenty of water or take rehydration fluids to avoid dehydration if diarrhea occurs.
- 5) Patients **should avoid** excessive sun exposure and use adequate sunscreen protection **if** sun exposure is anticipated.

#### **5.7.1.3 MK-2206**

- 1) MK-2206 **will be** administered orally at a dose of 200 mg weekly every four weeks.
- 2) Patients should take MK-2206 - 2 hours before or after a meal.
- 3) Patients should be instructed to store MK-2206 at room temperature.
- 4) Patients should be advised to **drink plenty** of water or take rehydration fluids to avoid dehydration if diarrhea occurs.

#### **5.7.1.4 Lapatinib**

- 1) Lapatinib will be administered orally **at a** dose of 1500 mg daily every three weeks.
- 2) Patients should take Lapatinib - 1 hour before or after a meal.
- 3) Patients should be instructed to store Lapatinib at room temperature.
- 4) Patients should be advised to drink plenty of water **or take** rehydration fluids to avoid dehydration if diarrhea occurs.
- 5) Routine monitoring for cardiac function (ECHO/MUGA) **should** be performed at baseline and every other cycle of treatment.

### **5.7.2 Other agents**

#### **5.7.2.1 Sunitinib**

- 1) Sunitinib will be administered orally at a dose of 50 mg daily for 4 consecutive weeks followed by 2 weeks of rest (drug holiday) with no sunitinib every 6 weeks.

- 2) Patients will take sunitinib once daily in the morning, with or without food, as desired.
- 3) Patients should be instructed to store Sunitinib at room temperature.
- 4) Patients should be advised to drink plenty of water or take rehydration fluids to avoid dehydration if diarrhea occurs.
- 5) Because hypertension is a known and potentially serious but rare adverse event associated with sunitinib malate treatment, patients will have their blood pressure monitored and recorded weekly during the first cycle of therapy, either at the doctor's office or using any calibrated electronic device (such as those found at a local drug store or pharmacy). (See Section 6 for hypertension management and dose reduction guidelines.)
- 6) Routine monitoring for cardiac function (ECHO/MUGA) should be performed at baseline and then every other cycle of treatment in the following groups of patients: (1) those entering the trial with NYHA Class II cardiac dysfunction (see [Appendix D](#)), (2) those with a history of Class II heart failure who are asymptomatic on treatment, and (3) in those previously exposed to anthracyclines or thoracic irradiation if the heart was included in the radiotherapy port. Routine cardiac monitoring is not required in patients with no known cardiac dysfunction at entry or in the absence of clinically observed adverse cardiac events.
- 7) Although adrenal gland insufficiency is rarely seen with sunitinib treatment, patients should be clinically followed for the signs and symptoms of this complication, especially (1) patients with comorbidities associated with adrenal dysfunction, (2) patients with pre-existing adrenal insufficiency (primary or secondary), and (3) patients with concomitant stress (e.g., fever, infection, bleeding, serious accident, surgery) that may precipitate overt adrenal insufficiency in the presence of subclinical sunitinib-induced adrenal toxicity. If clinically indicated, objective testing for adrenal gland function should be conducted.
- 8) Patients with bulky solid tumors should be monitored closely for pneumothorax, intestinal fistulae, or intestinal perforation in the event of rapid tumor destruction.
- 9) Patients should be alerted to the possibility that sunitinib capsules can cause a yellow discoloration of the skin on direct contact. If this happens, the patient should wash immediately with soap and water.

## **5.8 General Concomitant Medication and Supportive Care Guidelines**

### **5.8.1 General Guidelines: Concomitant Medications**

A concomitant medication is any medication a patient entering the trial is using and is expected to continue using for some portion of the trial as well as any medication the patient uses during the course of the trial. Study drugs are not considered concomitant medication.

All concomitant medications recorded at trial entry must have a related, ongoing concomitant illness listed under the medical history at the time of patient entry into the trial unless the medication is used for prophylaxis. Patients may continue to use any ongoing medications not prohibited by the protocol. All prescription and over-the-counter medications at trial entry as well as any new medications started during the trial must be documented. The documentation should continue until 30 days from the end of the last study drug treatment.

No other anti-cancer therapy including chemotherapy, radiation therapy, hormonal cancer therapy and immunotherapy, or experimental medications are permitted while the patients are receiving treatment under one of the targeted therapy arms of this trial. Any disease progression that requires other specific anti-tumor therapy will be cause for discontinuation from study medication. Patients who are receiving steroids for complications of their primary malignancy may enroll on the study and continue receiving steroids as long as needed. Because there is a potential for interaction of all of the medications used in the experimental arms, with other concomitantly administered drugs through the cytochrome P450 system, the case report form (CRF) must capture the concurrent use of all other drugs, over-the-counter medications, or alternative therapies. The Principal Investigator should be alerted if the patient is taking any agent known to affect or with the potential to affect selected CYP450 isoenzymes. A comprehensive list of CYP3A4 inhibitors, inducers, and substrates is provided (see **Appendix F**). In addition, patients and their caregivers should be provided the patient information sheet (see **Appendix G**) describing potential interactions of the study agents with other drugs, remedies, and medications.

Additionally, the patient's smoking history should be documented in the CRF, including the number of packs smoked/day (if a current smoker).

#### 5.8.1.1 Diarrhea

Diarrhea should be treated with the following regimen: loperamide (4 mg PO) at onset of symptoms, followed by 2 mg loperamide every 2 hours while awake (or 4 mg PO every 4 hours while sleeping) up to a maximum of 16 mg loperamide per day.

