### **6.1 CTEP agents**

#### **6.1.1 Erlotinib**

**Table 6. Erlotinib Monotherapy Dose Level Reductions**

Dose Level	Erlotinib Dose
Starting Dose	150 mg/day
First Dose Reduction	100 mg/day
Second Dose Reduction	75 mg/day

**Table 7.** Dosage Modification Criteria for **Erlotinib**–related Toxicities

Toxicity	Grade	Erlotinib dosage modification*	Guideline for management
Keratitis	1	None	No intervention
	2 (if < 14 days)	None	Preservative-free artificial tears, ointments, and/or other therapies as clinically indicated, with a follow-up examination within 2 weeks
	2 (if > 14 days)	Hold until recovery to $\leq$ grade 1 And then Reduce 1 dose level	
	$\geq 3$	Hold until recovery to $\leq$ grade 1 And then Reduce 1 dose level*	
Diarrhea	1	None	No intervention
	2	None if tolerable If not tolerable, hold until resolution to grade $\leq 1$ , then resume at the same dose. If intolerable grade 2 recurs after resumption, hold until resolution to grade $\leq 1$ and resume with 1 dose reduction.	Loperamide (4 mg at first onset, followed by 2 mg every 2–4 hrs until diarrhea free for 12 hrs)
	$\geq 3$ (despite optimal loperamide use)	Hold until recovery to $\leq$ grade 1 And then Reduce 1 dose level*	
Rash	1	None	No intervention
	2	None if tolerable If not tolerable, hold until resolution to grade $\leq 1$ , then resume at the same dose. If intolerable grade 2 recurs after resumption, hold until resolution to grade $\leq 1$ and resume with 1 dose reduction.	Any of the following: minocycline, topical tetracycline or clindamycin, topical silver sulfadiazine, diphenhydramine, oral prednisone (short course)
	$\geq 3$	Hold until recovery to $\leq$ grade 1 And then Reduce 1 dose level	

Bilirubin	$\geq 3 \times \text{ULN}$	Hold until grade $\leq 2$ And then Reduce 1 dose level	
Liver transaminase	$> 5 \times \text{ULN}$	Hold until grade $\leq 2$ And then Reduce 1 dose level	
Signs and symptoms of interstitial pneumonitis		Hold pending diagnosis Permanently discontinue if diagnosis is confirmed and considered possibly related to erlotinib	Patient should be thoroughly evaluated, closely monitored, and supported as clinically indicated
Other toxicity	$\geq 2$ prolonged clinically significant toxicity	Hold until recovery to $\leq$ grade 1 And then Reduce 1 dose level*	Treatment as appropriate

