### 6.1.2 AZD6244 Hyd-Sulfate

**Table 8:** AZD6244 Monotherapy Dose Level Reductions

Dose Level	AZD6244 Dose
Starting Dose	75 mg BID
First Dose Reduction	50 mg BID
Second Dose Reduction	50 mg once daily

**Table 9:** Dosage Modification Criteria for AZD6244-related Toxicities

Event	AE Grade or Observation	Dose modification
Dermatology/Skin	Grade 1 or 2	Maintain dose
	Grade 3 or 4 or intolerable grade 2	Hold AZD6244 until < tolerable grade 2, then reduce 1 dose level and resume treatment  .
	Recurrent Grade 3	Hold AZD6244 until < tolerable grade 2, then reduce 1 additional dose level and resume treatment  .

	Recurrent Grade 3 after 2 dose reductions	Remove patient from study arm.
	Grade 4	Patients with grade 4 rash (i.e. life threatening generalized exfoliative ulceration; erythema multiforme/toxic epidermal necrolysis should be removed from study arm.
V  Diarrhea  (if anti-diarrheal treatment is ineffective)	Grade 1 or 2	Maintain dose; continue anti-diarrheal treatment. Loperamide (4 mg at first onset, followed by 2 mg every 2–4 hrs until diarrhea free for 12 hrs)
	Grade 3 or 4	Hold AZD6244 until < tolerable grade 2, loperamide; reduce 1 dose level and resume treatment  .
	Recurrent Grade 3 or 4	Hold AZD6244 until < tolerable grade 2, loperamide; reduce 1 additional dose level and resume treatment  .
	Recurrent Grade 3 or 4 after 2 dose reductions	Remove patient from study arm.
Hematologic  (neutrophils, platelets, hemoglobin)	Grade 1 or 2	Maintain dose
	Grade 3 or 4	Hold AZD6244 until < grade 2, then reduce 1 dose level and resume treatment.
	Recurrent Grade 3 or 4	Hold AZD6244 until < grade 2, then reduce 1 additional dose level and resume treatment.
	Recurrent Grade 3 or 4 after 2 dose reductions	Remove patient from study arm.
Liver Function  (serum bilirubin, AST, or ALT)	Grade 1 or 2	Maintain dose
	Grade 3 or 4	Hold AZD6244 until < grade 2, then reduce 1 dose level and resume treatment
	Recurrent Grade 3 or 4	Hold AZD6244 until < grade 2, then reduce 1 additional dose level and resume treatment
	Recurrent Grade 3 or 4 after 2 dose reductions	Remove patient from study arm.
Other non-	Grade 1 or 2	Maintain dose

hematological toxicity	Any Grade 2 of concern (e.g., prolonged cardiac, pulmonary, or neurotoxicity, intolerable stomatitis)	Hold AZD6244 until < grade 1, then reduce 1 dose level and resume treatment

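### Section 5.8.1.1 caps loperamide at 16 mg a day, four dose-modification tables give an uncapped schedule (14 to 26 mg in the first 24 hours), and the diarrhea rules do not say which regimen counts

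*Combined protocol and SAP*

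**What the plan says.** Section 5.8.1.1, within the general supportive-care guidelines of Section 5.8, is not limited to any arm. It calls for "loperamide (4 mg PO) at onset of symptoms, followed by 2 mg loperamide every 2 hours while awake", allows 4 mg every 4 hours during sleep instead, and ends with the limit "up to a maximum of 16 mg loperamide per day".

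The dose-modification tables in Section 6.1 give their own regimen. Table 7 (erlotinib) starts with 4 mg, "followed by 2 mg every 2–4 hrs until diarrhea free for 12 hrs". Table 9 (AZD6244), Table 11 (MK-2206) and Table 13 (lapatinib) repeat that schedule. None of the four states a daily maximum or cites Section 5.8.1.1.

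The tables then make action on the study drug depend on how well loperamide has worked:

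- **Table 7:** the row for grade 3 or higher (hold, then reduce one level) carries the qualifier "despite optimal loperamide use".
- **Tables 9, 11 and 13:** the whole diarrhea row is labelled "if anti-diarrheal treatment is ineffective". Grade 3 or 4 leads to a hold and a one-level reduction, and recurrence after two reductions leads to removal from the arm.

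The documents do not define optimal or ineffective, and they do not say which loperamide regimen takes precedence.

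**The concern.** Two regimens for the same event stand side by side, one capped and one not. A clinician who works from the table for the patient's drug, as Section 6 directs for dose adjustment, can exceed the daily limit in Section 5.8.1.1 without any sign in the table that a limit exists.

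The second issue is interpretive. Whether diarrhea has persisted despite adequate loperamide decides whether the study drug is reduced, and repeated failure decides whether the patient leaves the arm. With two candidate regimens and no definition, two clinicians could classify the same patient differently. A later reader of the reported reductions and removals could not tell which standard had been applied.

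The event is not rare. The adverse event lists in Section 7.1.1 place diarrhea in the likely category (over 20%) for erlotinib, AZD6244 and lapatinib, and in the less likely category (20% or below) for MK-2206.

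**Working it through.** **Inputs.** First dose 4 mg at hour 0, later doses 2 mg, interval i of 2 to 4 hours, stop after 12 diarrhea-free hours (Tables 7, 9, 11 and 13). Cap 16 mg per day (Section 5.8.1.1). The cap is a stipulated limit, so there is no calculated figure of the plan's to reproduce.

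**First 24 hours.** Doses after the first fall at i, 2i, and so on, before hour 24, which makes 24/i − 1 of them. Total = 4 + 2 × (24/i − 1).

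| Interval | Later doses | First 24 h | Against 16 mg | Full later day, 2 × 24/i |
|---|---|---|---|---|
| 2 h | 11 | 4 + 22 = 26 mg | 10 mg over | 24 mg |
| 3 h | 7 | 4 + 14 = 18 mg | 2 mg over | 16 mg |
| 4 h | 5 | 4 + 10 = 14 mg | 2 mg under | 12 mg |

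Counting a dose at hour 24 as well gives 28, 20 and 16 mg, so the same two intervals exceed the cap.

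**When the cap is passed.**

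- Every 2 h: 4 + 6 × 2 = 16 mg at hour 12, and 18 mg at hour 14.
- Every 3 h: 4 + 6 × 2 = 16 mg at hour 18, and 18 mg at hour 21.
- Every 4 h: not within 24 hours.

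**How long symptoms must last.** Dosing continues until 12 hours after the last episode. The hour-14 dose of the 2-hour schedule is therefore due if diarrhea continues beyond hour 14 − 12 = 2. The hour-21 dose of the 3-hour schedule is due if it continues beyond hour 21 − 12 = 9. The full 26 mg needs the hour-22 dose, so diarrhea beyond hour 22 − 12 = 10, with dosing kept up through the night.

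**Which drugs.** The schedule appears in the tables for erlotinib, AZD6244, MK-2206 and lapatinib. Table 16 (sunitinib) has no diarrhea row, so sunitinib is not part of the conflict, although its own list also shows diarrhea as likely.

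**The case against.** The best reply is that silence is not contradiction. Section 5.8.1.1 is general, no table lifts its cap, and a careful reader could apply the cap to the table schedule. That reading is available and would remove the excess, but nothing in the text directs it. The tables give a complete regimen of their own, with a stopping rule based on symptoms and not on a daily total. Followed as written, they pass the cap at the two shorter intervals examined.

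Several stronger readings are tempting and are not supported:

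- **The tables always breach the cap.** At 4-hour intervals they total 14 mg. The 26 mg figure is the top of the range.
- **Following Section 5.8.1.1 means reducing the study drug sooner, so dose intensity falls.** No rule ties failure to a milligram total. Reduction depends on toxicity grade and on clinical judgement. At 4-hour intervals the table gives less loperamide than the cap allows, so the supposed direction reverses. The erlotinib rule for intolerable grade 2 diarrhea does not depend on loperamide at all.
- **The night-time instruction in Section 5.8.1.1 cannot be followed on the first day.** That depends on the hour of onset. With onset at 20:00 and sleep from 22:00, doses of 4 + 2 + 4 + 4 = 14 mg by 06:00 stay within the cap.
- **Practice now differs between sites.** Section 4.1.2 records that the participating site closed on 02/05/2015.

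It is also fair to object that little can change going forward. Sections 3.3, 5.3 and 16.4 record that the treatment arms closed on 3/22/2016. That limits the practical benefit, but the version dated 01/07/2020 still carries both regimens as current text.

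**Conclusion.** The inconsistency is real and confined to supportive care for four drugs. The table schedule runs from 14 to 26 mg over the first 24 hours against a stated cap of 16 mg. It exceeds the cap at 2-hour and 3-hour intervals if symptoms persist, and stays below it at 4-hour intervals.

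This assumes round-the-clock dosing and counts the first 24 hours from onset as one day. The 2-hour result does not depend on that counting, since a full later day still totals 24 mg. The 3-hour result does, since a full later day totals exactly 16 mg.

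The standard for reducing the study drug, or removing a patient, for diarrhea is ambiguous because neither adequacy term names a regimen. The documents do not establish whether this would raise or lower dose intensity, or by how much. Sample size, power and alpha are unaffected, and Section 15.5.2 keeps patients with incorrect treatment schedules in the response-rate analysis. No view is taken here on which regimen is right.

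**What to change.** Reconcile Section 5.8.1.1 and Tables 7, 9, 11 and 13 to one loperamide schedule with one stated daily maximum, chosen by the clinical team. Have each table refer to it, and define optimal use (Table 7) and ineffective treatment (Tables 9, 11 and 13) by reference to it.

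The cost is wording in one section and four tables. If any patient is still on study drug, this belongs in an amendment. If none is, a clarifying note is enough, stating which regimen was treated as the standard when diarrhea-related reductions and removals were recorded, or that none was fixed, so that those counts can be interpreted when reported.

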#### 5.8.1.2 Nausea and vomiting

The nausea and vomiting that may occur with investigational agents should be managed through the use of appropriate simple supportive measures (e.g., prochlorperazine or metoclopramide).

#### 5.8.1.3 Hand-foot syndrome

This may be treated with topical emollients (such as Aquaphor), topical or systemic steroids, and/or antihistamine agents. Vitamin B6 (pyridoxine; 50-150 mg orally each day) may also be used. Avoid exposure to heat, hot water, pressure, or friction. Use of soft, well-fitting shoes may help, as may use of acetaminophen if needed for analgesia.

#### 5.8.1.4 Rash

Rash should be treated with standard acne therapies, including topical and oral antibiotics used to treat acne such as the following: minocycline, topical tetracycline, topical clindamycin, topical silver sulfadiazine, diphenhydramine, or oral prednisone (short course).

#### 5.8.1.5 Other protective / preventative measures

Patients on Erlotinib should wear sunscreen protection, hat, and long sleeves to avoid sun as it can exacerbate skin rash.

##### 5.8.1.5.1 Myelosuppression related complications

Patients with neutropenic fever or infection should be evaluated promptly and treated with IV antibiotic therapy or therapeutic colony-stimulating factors as appropriate

following the ASCO guidelines [J Clin Oncol 18(20):3558-85, 2000]. Packed red blood cell and platelet transfusion should be administered as clinically indicated.

Erythropoietic agents may be used at the discretion of the treating physician.

#### 5.8.1.5.2 Additional recommendations for patients in Sunitinib arm

- Use of agents with proarrhythmic potential (terfenadine, quinidine, procainamide, disopyramide, sotalol, probucol, bepridil, haloperidol, risperidone, indapamide, and flecainide) is not permitted during treatment with this drug. A comprehensive list of agents with proarrhythmic potential can be found at <http://torsade.org> .
- Sunitinib is primarily metabolized by liver enzymes, particularly CYP3A4. Co-administration of potent inhibitors or inducers of this enzyme can result in significant changes in exposure to sunitinib (e.g., a mean 1.8-fold increased exposure with ketoconazole and a mean 4-fold decrease with rifampin). For this reason, use of the following agents is not permitted before or during enrollment in this arm of the study:

#### **Inhibitors – prohibited 7 days before dosing and during study.**

azole antifungals (ketoconazole, itraconazole)	Verapamil
clarithromycin	HIV protease inhibitors (indinavir, saquinavir, ritonavir, atazanavir, nelfinavir)
erythromycin	Delavirdine
diltiazem	

#### **Inducers – prohibited 12 days before dosing and during study.**

rifampin	Phenytoin
rifabutin	St. John's wort
carbamazepine	Efavirenz
phenobarbital	Tipranavir

- Steroid use is not recommended during sunitinib treatment unless absolutely necessary (e.g., for treatment of adverse events or protocol-required premedication) because many steroids (e.g., prednisone, prednisolone, dexamethasone, etc.) effectively lower sunitinib exposure through CYP3A4 interactions.
- The use of coumarin-derivative anticoagulants such as warfarin (Coumadin®) is not recommended, although doses of up to 2 mg daily are permitted for prophylaxis of thrombosis.

